4.1.2 Number of Participants

[figure not shown]
Up to 175 participants will be enrolled and 140 participants will be randomized at up to 15 US sites.

4.2 Study Objectives and Endpoints

[figure not shown]
The objectives of this study are to evaluate the safety and effectiveness of JUVÉDERM VOLBELLA XC injectable gel in adult participants seeking correction of infraorbital hollowing.

[figure not shown]
Each study objective is presented with corresponding endpoints below:

[figure not shown]
Objectives	Endpoints

Primary
 
• To evaluate the effectiveness of JUVÉDERM VOLBELLA XC injectable gel in adult participants seeking correction of infraorbital hollowing 
• To evaluate the safety of JUVÉDERM VOLBELLA XC injectable gel in adult participants seeking correction of infraorbital hollowing	
Primary Endpoint
 
• Responder rate on the AIHS at Month 3 after the last treatment. (A responder is defined as participants who show at least 1-point improvement from baseline on the AIHS in both infraorbital areas based on EI assessment. Baseline is defined as the EI assessment at screening.) 
Secondary Endpoints
 
• Responder rate on the GAIS at Month 3 by EI and participant. (A responder is a participant who has Improved or Much Improved on GAIS.)• Participant responses on the FACE-Q Appraisal of Lower Eyelids questionnaire 

[figure not shown]

5. Statistical Methodology and Study Endpoints

5.1 Statistical Methods Planned in the Protocol and Determination of Sample Size

This SAP will be approved prior to database lock. The SAP expands the statistical section of the [protocol](#) and contains a detailed description of methods to analyze data collected in the study. The text portion of the SAP will be included as an appendix to the CSR.

5.1.1 Statistical and Analytical Plans

Statistical analyses will be conducted using SAS Version 9.3 or newer.

5.1.1.1 Common Conventions

5.1.1.1.1 Analysis Periods

- Participants will receive treatment at the outset of the study (treatment group) or have treatment delayed until Month 3 (control group). The delayed treatment for control group is optional and referred to as “Optional Treatment”.
- Participants in the treatment group may receive optional touch-up treatment at Day 30 or optional repeat treatment at the completion of Month 12.
- Participants in the control group may receive optional touch-up treatment at Day 30 after optional treatment.
- Analysis periods are defined in [Table 5-1](#) below.

Table 5-1 Analysis period definition

Randomization Group	Period	Treatment Group Label	Start Date	End Date
Treatment	CP	VOLBELLA	Initial treatment date	The date of effective assessment for Month 3. 
 • If multiple assessments fall into Month 3 window, the date of the assessment included in the Month 3 analysis will be used as end date. • For participants who exit before Month 3, the end date is study exit date. • For participants with missing assessment at Month 3, the target day for Month 3 (Day 91) will be the end date.
	TP (12-Month)	VOLBELLA	Initial treatment date	Study exit date or date prior to repeat treatment, whichever is earlier
	Repeat Treatment Period	VOLBELLA	Repeat treatment date	Study exit date
Control	CP	Control	Randomization date	For participants who do not receive optional treatment: 
 • If multiple assessments fall into Month 3 window, the date of the assessment included in the Month 3 analysis will be used as end date. • For participants who exit before Month 3, the end date is study exit date. • For participants with missing assessment at Month 3, the target day for Month 3 (Day 91) will be the end date. For participants who receive optional treatment: 
 • The day before optional treatment
	TP (9-Month)	VOLBELLA Post-Control	Optional initial treatment date	Study exit date

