For initial treatment and touch-up treatment, details regarding anesthesia use, volume injected, kit numbers, whether needle or cannula was used, characteristics of the procedure (eg, subject assessment of procedural pain), and characteristics of the product (eg, TI evaluation of injection ease and moldability) will be recorded on the eCRF.

Concomitant medications, concurrent procedures, therapies, and AEs will be monitored continuously throughout the study. The procedures and evaluations for the treatment period are listed by visit in [Table 1](#).

For treatment group subjects, routine follow-up visits for safety and effectiveness will occur at Months 1, 3, 6, 9, and 12 after the last treatment (initial or touch-up). The procedures and evaluations for the follow-up period are listed by visit in [Table 2](#).

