5.1.1.6.1 Adverse Events

An AE will be considered a TEAE if:

- The AE began on or after the date of the first dose of study intervention; or
- The AE was present before the date of the first dose of study intervention, but increased in severity or became serious on or after the date of the first dose of study intervention; or
- For the control group, AE began on or after the date of randomization; or
- For the control group and prior to the initial treatment, if AE was present before randomization, but increases in severity on or after randomization date, the AE is considered as TEAE.

An AE will be considered a treatment-emergent SAE if it is a TEAE that additionally meets any SAE criteria.

AEs and encompassing abnormalities, reported as occurring after the Screening Visit, will be coded using MedDRA version 20.1 or newer. A listing for all TEAEs in the treatment and control groups will be presented. AEs that occur before initial treatment for the treatment group and randomization for the control group will be listed. Additionally, unique participants reporting AEs as well as the number of events in the following AE categories will be summarized for treatment participants, control participants after optional treatment, and all treated participants as follows:

Table 5-7 AE Summaries

Endpoint	Description	Timing	Methodology
Overall summary	Overall summary only for the following categories: 
 • TEAEs • Treatment-related TEAEs • Treatment-related TEAEs at injection site • Treatment-related TEAEs not at injection site • SAEs • Treatment-related SAEs • Treatment-related SAEs at injection site • Treatment-related SAEs not at injection site • Discontinued due to TEAE • Deaths 	
 • CP • TP (12-Month) • Repeat Treatment Period • TP (9-Month) 	Categorical counts, Event descriptive
TEAEs	
 • Overall Summary and by SOC, PT 		Categorical counts, Event descriptive
TEAEs	
 • Overall summary and by SOC, PT and severity 		Categorical counts, Event descriptive
Treatment-related TEAEs	
 • Overall summary and by SOC, PT 		Categorical counts, Event descriptive
	
 • Overall summary and by SOC, PT and severity 		
	
 • Summary by duration, time to onset, severity, causality, treatment required, and outcome 		

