6.1 Study Treatment Conventions

6.1.1 Analysis Days

Treatment day for effectiveness, ISR, and AE are defined as follows:

Table 6-1 Analysis Day Definitions

Term	Description
Effectiveness: Effectiveness Day	
JUVÉDERM VOLBELLA XC and control (only the control participants receiving optional treatment): Relative to the last treatment date (either the initial treatment, if no touch-up is performed, or the touch-up treatment, repeat treatment)
 
 • Effectiveness Day = analysis date - last treatment start date + 1 ○ Effectiveness Day 1 = last treatment start date 
Control (before receiving optional treatment): Relative to the randomization date
 
 • Effectiveness Day = analysis date - randomization date +1 • Effectiveness Day 1 = randomization date
Safety (including AE and ISR): Safety Day	
JUVÉDERM VOLBELLA XC and treated control (only the control participants receiving optional treatment): Relative to treatment date (initial and touch-up)
 
Safety Day = analysis date - treatment date + 1 Safety Day 1 = treatment date
 
Control (before receiving optional treatment): Relative to the randomization date
 
 • Safety Day = analysis date - randomization date +1 • Safety Day 1 = randomization date 
JUVÉDERM VOLBELLA XC Only: Relative to the repeat treatment date (after repeat treatment)
 
 • Safety Day = analysis date - repeat treatment date + 1 • Safety Day 1 = repeat treatment date

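### Control Period adverse-event counts compare arms followed for different lengths of time, and the visible plan makes no adjustment for exposure

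*SAP*

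**What the plan says.** **Treated arm.** SAP 5.1.1.1.1 (Table 5-1) starts the CP at the "Initial treatment date" and ends it at "The date of effective assessment for Month 3". SAP 6.1.1 (Table 6-1) counts effectiveness days "Relative to the last treatment date (either the initial treatment, if no touch-up is performed, or the touch-up treatment, repeat treatment", with "Effectiveness Day = analysis date - last treatment start date + 1". Protocol 6.2.3.1 agrees: "routine follow-up visits for safety and effectiveness will occur at Months 1, 3, 6, 9, and 12 after the last treatment". On touch-ups, Table 5-1's lead-in says "Participants in the treatment group may receive optional touch-up treatment at Day 30", and Protocol 4.3.4 places the touch-up 30 days after initial treatment. A touch-up therefore moves the end of the CP but not its start.

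**Control arm.** The CP starts at randomization. If optional treatment is declined, it ends at the Month 3 assessment. If it is accepted, the CP ends one day before that treatment, which Protocol 6.2.4.2 allows on the day of the Month 3 visit or up to two weeks later.

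**Missing Month 3 assessment.** In both arms, "the target day for Month 3 (Day 91) will be the end date".

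**AE summaries.** SAP 5.1.1.1.2 puts randomized controls in the safety population and uses that population for CP safety analyses. SAP 5.1.1.6.1 says that "unique participants reporting AEs as well as the number of events in the following AE categories will be summarized", and Table 5-7 lists the CP among its timings. The method given is categorical counts with an event description. The only exposure summary in the visible text is injected volume (SAP 5.1.1.5.1).

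**The concern.** After Month 3, controls either receive the device or leave the study. The CP is therefore the only period in which AEs under treatment can be set beside AEs in randomized participants who have not been treated. Crude counts support that reading only if both arms are watched for similar lengths of time.

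Here the treated window depends on a decision made after randomization by the participant and the Treating Investigator, namely whether to touch up. The control window depends on a different decision, namely whether and when to accept optional treatment. An unrelated background event has more chance of being counted in whichever arm is observed longer. A reader of the CP table could take a difference in follow-up for a device effect, or could miss a device effect that a difference in follow-up offsets.

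**Working it through.** The plan states no figure for these window lengths, so there is none to reproduce. All day counts are inclusive, with the start date as Day 1 (Table 6-1), and use nominal visit days because the analysis visit windows in Tables 6-2 and 6-3 are not shown.

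**Inputs**
- Month 3 target: Day 91 (Table 5-1).
- Touch-up: Day 30 (SAP), or 30 days after initial treatment, which is Day 31 (Protocol 4.3.4).
- Optional treatment of controls: 0 to 14 days after the Month 3 visit (Protocol 6.2.4.2).

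**Window lengths**
- Treated, no touch-up: 91 days.
- Treated, touch-up: (touch-up day − 1) + 91 = 29 + 91 = 120, or 30 + 91 = 121 days.
- Control, optional treatment declined: 91 days.
- Control, treated on the Month 3 visit day: 91 − 1 = 90 days.
- Control, treated 14 days later: 91 + 14 − 1 = 104 days.

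**Ratio of treated to control window for a pair of participants.** This is also the expected ratio of background event counts at equal daily rates.

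| Treated window | Control 90 d | Control 91 d | Control 104 d |
|---|---|---|---|
| Touch-up, 121 d | 1.34 | 1.33 | 1.16 |
| No touch-up, 91 d | 1.01 | 1.00 | 0.88 |

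**Arm averages.** The touch-up rate t is not given, so it is assumed over its full range. Mean treated window = 91 + 30t.

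| Assumed t | Mean treated window (days) | vs 90 d | vs 91 d | vs 104 d |
|---|---|---|---|---|
| 0% | 91 | 1.01 | 1.00 | 0.88 |
| 25% | 98.5 | 1.09 | 1.08 | 0.95 |
| 50% | 106 | 1.18 | 1.16 | 1.02 |
| 75% | 113.5 | 1.26 | 1.25 | 1.09 |
| 100% | 121 | 1.34 | 1.33 | 1.16 |

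If every control were treated at the two-week limit, the averages would be equal when 91 + 30t = 104, so t = 13/30 = 43%. Below that rate the control arm would be observed longer.

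**Effect on a crude percentage with no device effect.** Let p be an assumed background risk over 91 days with a constant hazard. The risk over d days is 1 − (1 − p)^(d/91).
- p = 10%: 11.3% over 104 days and 13.1% over 121 days.
- p = 20%: 22.5% over 104 days and 25.7% over 121 days.

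The 121-day figures apply to a treated participant with a touch-up. They are not typical values for the arm.

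**Missing Month 3 assessment.** Table 6-1 counts effectiveness days from the last treatment and safety days from the treatment date, initial or touch-up. Table 5-1 does not say which count its Day 91 uses. For a touch-up participant the CP then ends either 91 or about 120-121 days after initial treatment.

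**The case against.** **The comparison is only descriptive.** No between-arm AE test, difference or interval appears in the visible text. The lead-in to Table 5-7 does not name untreated controls, and Protocol 8.1 limits the safety population to treated subjects. The first part stands: no inferential conclusion rests on these counts, and the primary effectiveness analysis is untouched. The second part does not remove the point. Table 5-7 includes the CP, its note sorts terms by the treatment group and then the control group, and control AEs before and after optional treatment are summarised separately. Untreated-control AEs are therefore tabulated.

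**Most rows are hardly affected.** This stands. Six of the ten categories in the overall summary are treatment-related, and untreated controls should be at or near zero there whatever the window. The distortion concerns all-cause TEAEs, SAEs, discontinuations due to TEAEs, and deaths.

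**Timing can be partly recovered.** All TEAEs are listed, and treatment-related TEAEs are summarised by time to onset. But the all-cause rows have no such summary, and the onset formula gives no reference date for untreated controls.

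**Person-time may be specified elsewhere.** Table specifications are in a separate document, and some protocol safety text is redacted. The claim is therefore limited to what the visible plan says.

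**A tempting stronger reading.** A reader might infer that the treated arm is simply watched about a third longer, so that the error counts against the device and is safely conservative. The documents do not support that. The 1.33 ratio holds only for a touch-up participant against a 91-day control. Without a touch-up, against a control treated at the two-week limit, it is 0.88.

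**Conclusion.** The point holds in a limited form. As written, Tables 5-1 and 6-1 give a treated CP of about 91 or 120-121 days and a control CP of about 90-104 days, and Table 5-7 applies crude counts to both. The descriptive all-cause AE comparison is therefore confounded with follow-up time. The window ratio for a pair of participants ranges from about 0.88 to 1.34. The net size and direction for the arms are unknown, because the touch-up rate and the timing of optional treatment are not given.

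This rests on nominal visit days. The illustrated percentages also rest on assumed background risks and a constant hazard. The unanchored Day 91 rule is a separate, smaller gap in the same table. The change is worth making because it is cheap and this is the only display with an untreated randomized arm.

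**What to change.** 1. Keep the Table 5-1 periods. In Table 5-7, for the CP all-cause AE rows, add total participant-time per arm and exposure-adjusted rates: events, and participants with events, per participant-month. Say whether participant-time stops at the first event for the participant-based rate.
2. In Table 5-1, state whether Day 91 for a missing Month 3 assessment counts from the initial or the last treatment.

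The cost is SAP wording and one or two extra columns, with no change to data collection. The rates assume a roughly constant hazard. If events cluster soon after injection, longer follow-up dilutes the treated rate, so the crude counts should stay beside the rates.

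Cutting both arms at Day 91 should be at most a supplementary display. With a touch-up on Day 31, it leaves only 91 − 31 = 60 days after the last injection and moves later post-touch-up events out of the table that shows the control arm. Those events would then appear only in the 12-month treated-period table.

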5.1.1.1.2 Analysis Populations

The analysis populations will consist of participants as defined below:

Table 5-2 Analysis Populations

Population	Definition	Study Treatment
mITT	
 • Participants who were randomized to study treatment (treatment group), received at least 1 study device treatment, and had baseline and at least 1 post-treatment assessment of the primary effectiveness variable • Participants who were randomized to the control group and have baseline and at least 1 follow-up assessment of the primary effectiveness variable 	Randomized assignment
Safety	
 • Participants who were randomized to study treatment (treatment group) and received at least 1 study device treatment • Participants who were randomized to the control group 	Actual received ^a
VIT Population	
 • Participants who were randomized and received VOLBELLA treatment at the beginning of the Control Period 	Actual received
VRT Population	
 • Participants in the VIT population who received VOLBELLA repeat treatment 	Actual received
VOT Population	
 • Participants who were randomized to control group and received VOLBELLA optional treatment after the Control Period 	Actual received

^a If a randomized control participant does not receive the optional treatment, the actual received treatment will be assigned as control treatment.

Effectiveness analyses in the CP will be performed on the mITT population using the “as-randomized” assignment for each participant (i.e., if a participant randomized to the control group is treated inadvertently at the start of the study, the assessments for that participant will nonetheless be included in the control group analysis). Effectiveness analyses in the TP (12-Month) and Repeat Treatment Period will be performed on the VIT and VRT populations, respectively.

Safety analyses in the CP will be conducted on the safety population using the actual received treatment. Safety analyses in the TP (12-Month), Repeat Treatment Period, and TP (9-Month) will be performed on the VIT, VRT, and VOT populations, respectively.

5.1.1.1.3 Study Treatments

The following treatment groups are defined for this study:

- Study Treatment: JUVÉDERM VOLBELLA XC injectable gel
- Control Treatment: No-treatment

5.1.1.1.4 Statistical Methodology

When indicated, 95% 2-sided CIs and 2-sided p-values will be presented. Individual endpoint analyses may specify exceptions (additions or deletions) to these general definitions.

Descriptive statistics will be presented for key outcome measures. Categorical variables will be summarized with frequency and relative frequency. Continuous variables will be summarized by number of participants, mean, median, standard deviation, 1st and 3rd quartiles, minimum, and maximum. Where appropriate, 2-sided 95% CIs for population mean, or population proportion, will be provided as part of the descriptive summary. 2-sided p-values will be presented when indicated.

Raw and derived data listings will be provided, and will be fully defined in the table, figure, and data listing specification document.

5.1.1.1.5 Missing Data

Missing data handling conventions for the primary endpoint is specified and summarized as follows:

Table 5-3 Missing Data Handling by Endpoint Type

Parameter type	Timing	Missing Data Handling
Responder	Month 3 (treatment period for treatment group and control period for the control group)	
 • All participants included (mITT population) • Multiple imputation with 5 imputed datasets is applied to participants with no Month 3 values using the below model: $\text{Month 3 AIHS} = \beta_0 + \beta_1 \text{Baseline AIHS} + \beta_2 \text{Month 1 AIHS}$. This is performed by treatment group and by side (left and right).
Responder	Month 3 (treatment period for treatment group and control period for the control group)	
 • All participants included (mITT population) • LOCF for participants with no Month 3 values

Note: Missing baseline will be replaced with the average of all non-missing baseline values of all participants.

5.1.1.1.6 Site Pooling

The impact of investigational sites on the primary effectiveness analysis at Month 3 will be evaluated by including investigational site, treatment assignment, and their interaction as predictor variables in a multivariable logistic regression analysis with response status on the AIHS as the dependent variable. The interaction between site and treatment will be considered significant if the p-value of this interaction is less than 0.10. Investigational sites with few enrolled participants may be pooled with other sites based on participant enrolled, geographical region, or other site characteristics.

5.1.1.2 Demographics

5.1.1.2.1 Analysis Populations

Number of participants in each analysis population (described in [Section 5.1.1.1.1](#)) will be provided using all randomized or treated participants.

5.1.1.2.2 Participant Disposition

Study disposition including number of participants screened, randomized, treated, received touch-up treatment, repeat treatment, completed, discontinued from the study, as well as eCRF-reported reasons for discontinuation will be summarized using all screened participants.

5.1.1.2.3 Protocol Deviations

Protocol deviations will be defined in a separate document, including significance classification. Significant protocol deviations will be summarized using all randomized or treated participants.

5.1.1.2.4 Demographics

Demographics including age, sex, race, ethnicity will be summarized for the Safety Population in total and by treatment group.

5.1.1.2.5 Baseline Characteristics

Baseline characteristics will be summarized in total and by treatment group for the Safety populations as follows:

- Weight (kg), height (cm), and BMI (kg/m²)
- Sun exposure (hours per day)

- Fitzpatrick skin phototype (each phototype, and by phototype groups, ie, I and II, III and IV, V and VI)
- Smoking history (status, tobacco product, frequency, and duration in months)
- Transient puffiness

5.1.1.2.6 Medical and Surgical History

Medical and surgical history as well as physical findings reported as occurring before the Screening Visit, will be coded using the Medical Dictionary for Regulatory Activities (MedDRA), Version 20.1 or newer. Participants who report medical and surgical history events that are ongoing at screening and not ongoing at screening will be summarized separately for the Safety population.

5.1.1.2.7 Prior and Concomitant Medications

Medications will be coded using the WHO Drug Dictionary, version MAR2017 or newer. Prior and concomitant medication will be presented in a data listing using the Safety population.

Table 5-4 Medication

Parameter	Description
Prior medications	Medications taken before the study treatment start date and time for the treatment group and before randomization date and time for the control group, regardless of medication end date
Concomitant medications	Medications taken on or after the study treatment start date and time for the treatment group and after randomization date for the control group, regardless of medication end date

If a medication’s start date and stop date are missing or the start date is before the first study treatment start date and stop date is missing or after the first study treatment start date for treatment group or after randomization date for control group, the medication will be considered as both prior and concomitant medications.

